We will acquire lower extremity and trunk muscles surface EMG activity and kinematics bilaterally during all experimental conditions. We will also use fine-wire EMG to acquire activity from the ilio-psoas, extensor hallicus longus, extensor digitorum longus and other deep muscles muscle. We will also record individual limb loading and level of BWS during standing and stepping conditions. We may acquire continuous blood pressure with a finger cuff, breathing rate using an elastic band place loosely around their chest and temperature with 1-3 small sensors taped over their skin above and below their injury level.

Locomotor Training Intervention.

Individuals with SCI will participate in 80 sessions of weight bearing step-training (n=10) for approximately 16 - 20 weeks (60-90 minutes/session, 3-5 sessions/week) during which the individuals may be placed on the treadmill in an upright position and suspended by an overhead pulley (Innoventor, St. Louis, MO) in a harness (Robertson, Hendersen, NV). During stepping using BWST and manual assistance the maximum load will be used that avoids knee-buckling and trunk collapse [64]. A trainer positioned behind the research participant will aid in pelvis and trunk stabilization, as well as weight shifting and hip rotation, and trainers positioned at each limb will provide manual assistance using a customized technique that facilitates knee extension during stance (by manually

stimulating the patellar and Achilles' tendons) and knee flexion and toe clearance during swing (by manually stimulating the hamstrings and tibialis anterior tendons). Trainers provide assistance only when needed. Individuals will step at a normal walking speed for their height and age (0.89 m/s – 1.34 m/s) and at the maximum body weight allowed with minimal force needed by the trainers to assist during stance (4, 25). Body weight support will be continuously reduced over the course of the 80 sessions as the individuals increase their ability to bear weight on the legs during stepping. Step training sessions might progress to the overground environment when appropriate.

Participants may also stand train in a stand training device, based on optimal parameters acquired during the initial phase of training. The participant might be asked to follow a supine and/or stand training home program (in a standing frame or similar device) once independence is achieved with the stimulation. The home program will only be used as a complement to the daily outpatient training sessions, and will be closely monitored by the research team. The research participants will have to demonstrate independence and safe use of the patient programmer in the lab prior to initiation of the home program. Parameters loaded in the patient programmers will only include those that have been used safely and result in supine movements or independent standing by the research participant in the laboratory setting. In addition, family members and caregivers will be trained on appropriate techniques to provided assistance as needed during home-based training. Independent standing and availability of caregivers to provided assistance in the home environment will be key factors when developing the home program.

We will collect electromyography (EMG), joint angle, and footswitch data at 1000 Hz using a 24-channel hard-wired analog to digital board and a custom written Labview software acquisition program (National Instruments, Austin, TX) during stepping using BWST or overground and manual assistance. EMG data will be sampled from 0.1 to 1 kHz and AC coupled into a differential amplifier (Konigsberg Instruments, Pasadena, CA). Following standard skin preparation, bipolar surface EMG electrodes with a fixed distance between the electrodes will be placed on the soleus, medial gastrocnemius, tibialis anterior, medial hamstrings, adductor, vastus lateralis, and rectus femoris bilaterally. Limb kinematics will be digitally acquired a passive marker high speed motion capture system (Motion Analysis, Santa Rosa, CA). Individual limb loads will be measured with shoe-insole pressure sensors (FSCAN, Tekscan, Boston). Data will be processed and synchronized using Labview software (National Instruments, Austin, TX) customized by our laboratory. EMG data will be full wave rectified and filtered using a 4th order bandpass Butterworth filter (40 Hz - 500 Hz). Mean EMG represents the relative number and frequencies of the motor units recruited per burst. Integrated EMG assesses the total EMG activity generated per step. EMG mean and integrated amplitudes from each muscle will be compared before and after locomotor training. Co-activation values of flexors and extensors will be calculated. The degree of coordination in the stepping-related oscillations of lower limb segments will be assessed through principal component analysis. Quantitative measurements and statistical testing have been described in detail in previous publications listed above.

Heart rate will be monitored using a digit pulse oximeter placed on the index finger of the research participant during training sessions and experiments.

Next analytical approaches will be utilized in these studies:

- **EMG burst cycle analysis.** EMG signals will be band pass filtered between 40-500 Hz to eliminate any transient signals and then rectified. A minimum threshold for EMG activity (3 standard deviations (SD) above mean baseline noise) will be selected for each channel. Onset of EMG bursts is detected as the location where the signal amplitude remains above the threshold for 50 continuous samples, and the end as the location where the signal amplitude remains below the threshold level for 150 continuous samples. Detected start and end points are displayed as marks on the data for verification. Mean EMG (MEMG) may be used to make interpretations about the relative number and firing frequencies of the motor units recruited per burst. Integrated EMG (IEMG) assesses the total EMG activity generated per step.
- **Muscle co-activity and clonicity.** We developed a method to quantify the clonicity of and coactivation among muscles during human locomotion based on a Bayesian approach to EMG analyses, using reversible jump Markov chain Monte Carlo (RJMCMC) simulation ([name] et al. 1997). In Bayesian analyses, data are passed through a simulation algorithm multiple times (300,000), generating distributions of the quantities of interest. The Bayesian process yields an objective assessment of the mean and deviation of parameters of a signal (in this case co-activity and clonicity), thereby, minimizing research participative error. Further, the measures vary less than 0.5% after repeating the measures three times across five data sets. This approach allows for statistically valid inferences about these quantities and the differences between them.
- **Linear envelopes.** The high-pass filtered and rectified EMG data will be low-pass filtered at 5 Hz. EMG bursts may be averaged relative to the start of a burst in the muscle, the start of a burst in another muscle, or to a biomechanical event such as the rise or decline of force. Averages will be generated from data normalized to the duration of each burst or step cycle. Averaged waveforms are of interest because they may be assumed to represent the typical activity pattern. Coefficients of variation will be calculated to scale standard deviations to a mean value throughout the step cycle.
- **Scatter plots.** Scatter plots will be used to detect relationships among muscle EMG, limb loading, stepping velocity, and joint position. Scatter plots will be generated from individual steps and averaged waveforms. EMG amplitudes (5 Hz low pass filtered) of agonist and antagonist muscles will be plotted (triceps surae (TS), tibialis anterior (TA), hamstring (HM), quadriceps (Q), and adductor (ADD) to assess muscle coordination. This provides information about the phasing of a muscle activity relative to other muscles. The relationship between EMG activity and either phases of loading or joint position will also be plotted. Three-dimensional relationships incorporating two of the latter variables and muscle EMG will also be utilized.
- **Voluntary response index.** Voluntary motor task EMG from healthy individuals has been averaged across a five second window to generate response vectors (RVs). The prototype response vector (PRV) was generated by normalizing the RVs by the vector magnitude and then averaged. The PRV is comprised of 10 elements, one for each

muscle. A PRV is created for each phase of each movement in the voluntary motor task component of the BMCA protocol. A similarity index (SI) is then used for comparison of the data. The SI is a numerical expression of the similarity of the distribution of the EMG activity in the RV, computed as the normalized dot product between the two vectors (vector representing the distribution of activity generated by healthy research participants, and that representing the distribution of activity in the test research participant). A value of 1.0 for the SI represents an identical distribution.

- Kinematic and kinetic analysis. Joint kinematics will be analyzed using EVaRT and Orthotrak which provide instantaneous 3-D graphic displays and all kinematic parameters of the motion performed by a research participant. The force signals will be acquired from FSCAN at 50 Hz and interpolated to 1000 Hz and low-pass filtered (5 Hz). A minimum threshold (3 SD above baseline) will be calculated for each signal. BWS was acquired by Labview A/D and processed by customized software.

These results will reveal whether conventional electrodes can be used to facilitate stepping in clinically complete spinal cord injury patients. This study will clarify whether the optimal spinal cord sites for using epidural stimulation to induce stepping and standing migrate over the course of training in the human spinal cord. We expect that these data will provide further evidence of the plasticity of the injured spinal cord, and that training modifies the spinal networks for stepping. Stepping performance of the patients will be compared against historical controls that were given step training without epidural stimulation. The criteria for success of the combined treatment will be determined by the best outcomes that have been obtained for previous patients who were only trained.

h. Treatment regimen(s) (*for medically invasive research*)

i. Clinical information (when applicable) (*for medically invasive research*)

j. Statistical analysis of the collected data

No statistical analysis will be used for comparison of data. This study is designed as a proof of principle study without statistical power to demonstrate the feasibility of the methods.

k. Data and Safety Monitoring Plan

Entity responsible for monitoring is identified:

The study will be monitored by a Data Safety Monitoring Board consisting of: [name] (Neurosurgeon), [name] (physiatrist); [name]

[name] (cardiologist) and [name] (Urologist) who are not associated with the study.

Policies and procedures for adverse event reporting are described:

If a subject develops an adverse event it will be reported to the DSMB, local IRB and Sponsor within 24 – 48 hours of being notified of the event.

Protocol Compliance:

Any deviations in the protocol will be documented and reported to the IRB.

Plans for measuring appropriate intervals between safety reviews and predetermined criteria for stopping the study:

Research participants will be continuously monitored for complications, adverse events and/or serious adverse events. If any complications arise during the course of the study the local Medical Advisor ([name]) will be notified. All study procedures will be halted until the complication, adverse event and/or serious adverse event has been reviewed by the medical advisor and it has been determined that it is safe for the study participant to return to participating in study procedures.

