We propose that daily locomotor training in the presence of SCES will enable the individual with clinically complete SCI to stand and step independently while bearing full weight. Non-patterned electrical stimulation of the lumbar spinal cord can induce patterned, locomotor-like activity in individuals with clinically complete SCI [1]. Modifying the frequency of stimulation can induce extensor patterns similar to that observed during standing [45]. In addition, when afferent information is also provided there is further modulation of these motor patterns elicited by epidural stimulation [46]. Individuals with a clinically complete spinal cord injury can execute independent steps using a body weight support system on a treadmill (BWST) using manual assistance without epidural stimulation. When combined with SCES, we anticipate the training will be even more successful, enabling prolonged periods of independent stepping and standing. Although there will not be a separate control group studied simultaneously, historical controls will consist of the best stepping and standing performance that have been observed previously in our laboratory in individuals that have a clinically complete SCI. Performance beyond this threshold by any individual treated with both epidural stimulation and training will be interpreted as a significantly better intervention than training alone.

Future studies will eventually focus on development and implementation of the more advanced multi-electrode array technique that will provide functionally-adaptive site-specific stimulation. The adaptive stimulation strategy proposed here takes advantage of capabilities of our new array design that are not possible using either conventional or commercially available electrode arrays. Our future arrays will provide two key benefits:

- Our electrode arrays cover a larger area than commercially available arrays, extending from the midthoracic to the sacral extents of the spinal cord. It is possible that the optimal stimulation sites for facilitating stepping versus standing may be spatially distinct on the spinal cord. If this is the case, conventional arrays are less likely to be able to recover both stepping and standing in the same patient.

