and discontinue their participation at any time without penalty. [name] will answer any questions with the potential research participant and/or family members who may have a relationship with them regarding the physical rehabilitative aspects of the research.

[name] or [name] will discuss the surgical protocols and the risks and benefits with the potential research participant. They will verbally review the surgical procedures and show the individual the stimulating and recording equipment that will be implanted. [name] or [name] will review all testing that will be conducted during the surgical procedures and explain to the potential research participant that s/he can refuse any of the procedures and discontinue their participation at any time without penalty. [name] or [name] will answer any questions with the potential research participant and/or family members who may have a relationship with them regarding the surgical procedures and the research.

[name] will determine study eligibility based on the inclusion and exclusion criteria and in accordance with the medical recommendation of Drs. [name], and Drs. [name] or [name]. [name] will also encourage potential research participants to read the informed consent and take several days to discuss participation with friends and family before agreeing to enter the study. Drs. [name], [name], and [name] will explain to the potential participant that the initial enrollment involves a series of pre-experiments and 80 step/stand training sessions and the results are necessary to determine if they are an appropriate candidate for the surgical component of the study. Participating in the initial portion of the study does not guarantee their eligibility for surgical implantation and epidural stimulation.

The screening informed consent will be written in at an 8th-grade language level and will contain information on all evaluations to be performed as well as contact information should the research participant or his/her associates have any further questions. The original signed informed consent and two copies will be kept in [name] office.

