All research participants, irrespective of age or sex, will meet the following criteria: 1) stable medical condition without cardiopulmonary disease or dysautonomia that would contraindicate standing or stepping with BWST; 2) no painful musculoskeletal dysfunction, unhealed fracture, contracture, pressure sore, or urinary tract infection that might interfere with stand or step training; 3) no clinically significant depression or ongoing drug abuse; 4) no current anti-spasticity medication regimen; 5) non-progressive SCI above T10; 6) must not have received botox injections in the prior six months; 7) be unable to stand and step independently overground; 8) unable to voluntarily move all individual joints of the legs; 9) at least one-year post injury; and 10) must be at least 18 years of age. In addition, all subjects must satisfy each of the three conditions of the functional neurophysiological assessment described below.

Additionally, research participants with the following characteristics will not undergo any assessments using transcranial magnetic stimulation (TMS): 1) metal in head (except mouth) such as but not limited to cochlear implant, implanted brain stimulators, aneurysm clips; 2) increased intracranial pressure (which lowers seizure thresholds); 3) cardiac pacemakers; 4) implanted medication pumps; 5) intracardiac lines; 6) significant heart disease; 7) history of stroke or other brain lesions; 8) personal or family history of epilepsy; 9) receiving tricyclic antidepressants or neuroleptics (which lower seizure threshold); 10) heavy alcohol consumption within past 48 hours

Functional Neurophysiological Assessment (FNPA). We will use FNPA to screen potential research participants based on specific neurophysiological inclusion criteria. Participants must have no volitional control of movement below the level of the lesion, but must retain some brain influence on spinal reflexes. Our target population, which will be identified by FNPA, cannot be identified reliably using traditional assessments: hence individual subjects may be classified widely as Class A, B, or C on the ASIA SCI scale. We will include only subjects who fulfill the following three requirements:

1. There is no descending volitional control of movement below the lesion
2. Segmental reflexes remain functional below the lesion
3. Brain influence on spinal reflexes is retained

G. Design/methodology including all survey instruments, questionnaires, etc.

SCREENING CONSENT:

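### One participant beyond the laboratory's historical best cannot support the conclusion that stimulation plus training is superior to training alone

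*Protocol*

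**What the plan says.** Section A (Background) says that there is no concurrent control group. The historical control is the "best stepping and standing performance that have been observed previously in our laboratory in individuals that have a clinically complete SCI". If any individual treated with stimulation and training exceeds it, this "will be interpreted as a significantly better intervention than training alone".

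The last paragraph of section G (Design/methodology) returns to the comparison: "Stepping performance of the patients will be compared against historical controls that were given step training without epidural stimulation". It then bases success of the combined treatment on the "best outcomes that have been obtained for previous patients who were only trained".

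Section j (Statistical analysis) states: "No statistical analysis will be used for comparison of data". It describes a proof-of-principle study without statistical power.

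Section F sets the sample at ten and selects participants by a functional neurophysiological assessment (FNPA). Under it, "individual subjects may be classified widely as Class A, B, or C on the ASIA SCI scale", and one of three required conditions is: "Brain influence on spinal reflexes is retained".

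Section D (Screening) and Stage 1A give each participant 80 training-only sessions and repeat the measurements afterwards. Section D says of this phase that "the results are necessary to determine if they are an appropriate candidate for the surgical component of the study". Stage 2A adds 160 sessions with stimulation.

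**The concern.** This is the only success rule in the protocol. The walker or cane in section F is a hoped-for benefit, and the independence and weight-bearing minutes in section D decide which sessions count.

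The rule turns one person's result into a comparative claim about the intervention. It has no margin, no stated number of controls and no allowance for ten participants each having a chance to pass. Section j disclaims formal comparison and power but does not withdraw the conclusion in section A. If the plan is followed as written, superiority over training alone could be declared when the best participant was simply a good responder to training, or differed from the controls in selection or in amount of training.

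**Working it through.** **No figure to reproduce.** The protocol gives no alpha, power or derivation for n = 10. The check is therefore an illustration plus a comparison of the sections.

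**1. Chance of meeting the rule with no stimulation effect.**
- Input from the protocol: 10 participants (section F), and one exceedance is enough (section A).
- Assumed: N controls (the number is not stated), drawn from the same population, and a continuous outcome without ties.
- All 10 + N people are then equally likely to hold the top value. The chance that the holder is a participant is 10/(10+N).

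| Assumed N | Calculation | Chance |
|---|---|---|
| 10 | 10/20 | 50% |
| 20 | 10/30 | 33% |
| 40 | 10/50 | 20% |

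To bring the chance down to 5%, N would have to be 10/0.05 − 10 = 190 comparable controls. If the outcome can tie, strict exceedance is less likely, so 10/(10+N) is then an upper limit.

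**2. Effect of non-comparable groups.** Assume normal outcomes, N = 20, and participants whose training-only mean differs from the controls' by 0.5 SD. The 33% becomes about 59% if participants are better and about 14% if they are worse. The shift is an assumption; the protocol offers no basis for its size or sign.

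**3. What is known of the two groups.**

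| Feature | Participants | Historical controls |
|---|---|---|
| Entry | FNPA conditions, ASIA A, B or C (section F) | Clinically complete (section A); only trained (section G) |
| Second selection | Results of screening and 80 sessions inform surgery (section D) | None stated |
| Training | 80 + 160 = 240 sessions | Amount not stated |

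Section F itself says that traditional assessments do not reliably identify its target population. A label of clinically complete therefore does not establish a match.

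**4. The outcome that sets the bar.** Section A names stepping and standing. Section G names stepping, then outcomes in general. Neither says whether one task is enough or both must be exceeded.

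**5. A reference already in the plan.** Each participant is re-measured after the 80 training-only sessions. Neither section A nor section G uses this result in the success rule.

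**The case against.** The strongest reply is that this is a declared proof-of-principle pilot. Historical controls are a legitimate choice there, and a best-ever bar is stricter than a control mean. The hoped-for effect, prolonged independent standing and stepping, is also large beside the brief training-only performance described in section A. An analysis plan not shown here may define the controls and the measure. All of this stands as a defence of using historical controls. It does not defend the conclusion drawn from them: the rule asks for no large margin, the bar is demanding only if the controls are numerous and comparable, and section A states the superiority reading itself.

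Several stronger readings are tempting but unsupported:
- A reader might infer that the controls are known to differ from the participants. The protocol is silent on their FNPA status, selection and training; silence is not contradiction.
- A reader might infer that the bias favours stimulation. Retained brain influence or more training could favour participants, while selection for non-response and a best-ever bar could work against them.
- A reader might infer that sections A and G describe different control groups. Section A ends by comparing with training alone, so the two can largely be read together. Only the outcome stays open.
- A reader might infer that the open outcome alone moves the chance across a very wide range. That depends on how stepping and standing correlate within a person. At N = 20, every reading gives 33% under full correlation. At an assumed correlation of 0.5, simulation gives 9% if one person must exceed both and 52% if either counts.
- The absence of a formal test in a pilot is not itself a fault.

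**Conclusion.** The point holds as a fault in the stated inference. One of ten participants beyond the historical best does not show superiority over training alone, and the disclaimer in section j does not repair the sentence in section A.

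The 50%, 33% and 20% are illustrations. They rest on an assumed N, exchangeable groups and a continuous outcome, and they describe the best-of-10 against best-of-N rule rather than any proven imbalance. Comparability of the controls is unverified, and neither the direction nor the size of any bias can be derived. The textual finding does not depend on these figures. The study can proceed, but its success rule should be changed.

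**What to change.** 1. In section A, delete the statement that one participant beyond the historical best shows a significantly better intervention. In section G, remove the historical best as success criterion.
2. Keep the historical best as descriptive context, with the same control description in both sections and the same outcomes: stepping and standing, each reported separately.
3. Name each participant's own result after the 80 training-only sessions (section D, Stage 1A) as the main training-alone reference. Report it beside the tests with and without stimulation.
4. Reconcile section D, where the post-surgery tests *will* be repeated, with Stage 1C, where they *may* be.
5. State the limits of this reference: possible selection for non-response to training, regression to the mean, and 160 further sessions mixed with stimulation.

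Cost: wording changes in sections A, D and G. The measurements after 80 sessions are already planned. Making the post-surgery tests firm may add assessments that Stage 1C leaves optional, at 1 to 4 hours per measurement by the protocol's own figure. The main downside is a narrower claim: the study would describe what participants achieved against their own training-only result and would not declare superiority.
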